9.7 DATA ANALYSIS

9.7.1 Primary analysis

The primary analysis population will include all women enrolled in the study prospectively who meet the study inclusion criteria and have pregnancy outcome data recorded. Outcomes for the primary analysis population will primarily be compared with pregnancy outcomes in unexposed external comparison groups. Ascertainment of pregnancy outcomes will be considered completed when:

- Pregnancy outcome is known and was not a live birth, or
- Pregnancy outcome was a live birth and the 1-year post-delivery follow-up has been completed, or
- The woman has been classified as lost to follow-up, or
- The woman has withdrawn informed consent prior to ascertainment of pregnancy outcome.

Otherwise, the pregnancy outcome will be considered as pending.

9.7.2 Secondary analysis

For the final analysis, descriptive analyses of baseline characteristics of the population of all prospectively enrolled women (including women whose pregnancy outcome data are unknown, such as lost to follow up), and the subset of women whose pregnancy outcome data are unknown, will also be calculated. Additional descriptive analyses will be provided on patient characteristics for the retrospectively collected pregnancies separately.

16-Nov-2016 Version number: 1

9.7.3 Interim analysis

Not applicable.

9.7.4 Analysis variables

Definitions of pregnancy outcomes are consistent with, but not limited to, definitions used by the Center for Disease Control and Prevention Metropolitan Atlanta Congenital Defects Program (CDC MACDP), the National Center for Health Statistics (NCHS), and Organization of Teratology Information Specialists (OTIS) (2,11). Overall pregnancy outcome will be classified into one of the following mutually exclusive categories: spontaneous abortions, induced abortions/elective terminations, stillbirth, preterm birth and live birth. Every birth defect identified in a live birth will be classified into major or minor congenital malformation.

Other outcomes of interest are: minor congenital malformations, preterm birth, small for gestational age at birth, and any other adverse pregnancy outcomes. The study will endeavor to assess all pregnancy outcomes for the presence of malformations and functional deficit in the infant up to 1 year of age. A detailed description of pregnancy outcomes is provided in Appendix A.

Additional analysis variables such as maternal age, smoking status during pregnancy, and maternal comorbidities may be included in analyses as important confounders or in subgroup analyses. These additional variables will be fully described in a separate statistical analysis plan which will be developed and finalized prior to database lock.

9.7.4.1 Main criteria

Main criterion is rate of spontaneous abortion in the prospectively collected LEMTRADA-exposed group versus comparison cohorts of pregnancies from women with and without MS who were not exposed to LEMTRADA. Descriptive statistics of maternal and pregnancy characteristics and the timing of exposure will be provided for retrospectively collected cases of spontaneous abortions to qualitatively describe this patient population.

9.7.4.2 Other criteria

Other criteria are rates of major and minor malformations will be classified according to the MACDP (2) for women exposed to LEMTRADA during pregnancy ascertained through the first year of life of the infant. The rates of the prospectively collected cases will be compared with corresponding rates in unexposed external comparison groups. Descriptive statistics of maternal and pregnancy characteristics as well as the timing of LEMTRADA exposure will be provided for retrospectively collected cases of congenital malformations. These retrospectively collected cases will also be examined (by the birth defect evaluator) to determine if there is a specific pattern of malformations observed with LEMTRADA exposure.

Additionally, pregnancy outcomes (stillbirth, elective terminations, preterm birth), small for gestational age at birth, and any other adverse pregnancy outcomes for women exposed to LEMTRADA during pregnancy are included. Malformations will be classified according to the MACDP (2). These rates of the prospectively collected cases will be compared with corresponding rates in unexposed external comparison groups. Maternal and pregnancy characteristics, as well as the timing of exposure, will be described qualitatively for retrospectively collected cases of the other pregnancy outcomes.

9.7.4.3 Criteria obtained from comparison cohorts

The following comparison groups in the AUBAGIO® (teriflunomide) North American pregnancy exposure registry (Genzyme study OBS13499) will be used:

- Cohort II (North American AUBAGIO Pregnancy Outcome Exposure Registry Cohort II) -pregnant women with MS not exposed to AUBAGIO during the current pregnancy modified to also exclude women exposed to LEMTRADA
- Cohort III (North American AUBAGIO Pregnancy Outcome Exposure Registry Cohort III) pregnant women without MS and not exposed to AUBAGIO during the current pregnancy modified to also exclude women exposed to LEMTRADA

NOTE: Cohort I (pregnant women with MS exposed to AUBAGIO) are excluded

Patient-level data from the AUBAGIO pregnancy registry are made available to the sponsor (Genzyme, a Sanofi Company) when data has been stripped of personal identifiers.

Following variables will be collected:

- Maternal age
- Maternal race/ethnicity
- Socioeconomic status
- Prior pregnancy history: gravidity/parity and previous outcomes
- Periconceptional use of folic acid containing supplements
- Unintended pregnancy
- Gestational age at enrollment
- Exposure to other medications (including known teratogens) and other MS medications
- Comorbidities
- Disease severity measure(s)

9.7.5 Statistical methods

Endpoints are prospectively collected rates of spontaneous abortion, major and minor congenital malformations, stillbirth, elective terminations, preterm birth, small for gestational age at birth, and any other adverse pregnancy outcomes for women exposed to LEMTRADA during pregnancy.

All the comparisons below between women exposed to LEMTRADA during pregnancy (prospectively collected) and unexposed comparison groups will be carried out separately against each comparison group.

Rates and 95% CI will be calculated. Rates will be compared between women exposed to LEMTRADA during pregnancy (prospective) and women in unexposed comparison groups by calculating the relative risk (RR) and its 95% CIs. As the majority of the events rates are anticipated to be low, when applicable, comparisons will be conducted using exact statistical methods.

A supportive analysis of (prospective) spontaneous abortion as a time-to-event endpoint will be conducted using the Kaplan-Meier method adjusting for left-truncation. If data are available, propensity score matching and covariate adjustment may be used in the Cox regression context with left-truncation to adjust for potential confounding factors, such as gestational age at enrollment, comorbidities, prior birth defects/abnormalities, exposure to other medications, etc.

For other endpoints (prospective), if data are available, propensity score matching and covariate adjustment may also be used in the logistic regression context to adjust for potential confounding factors. These approaches will reduce the influence of risk modifiers in determining the event risk ratio between Lemtrada-exposed women and non-Lemtrada-exposed women.

Qualitative descriptive statistics on maternal and pregnancy characteristics and the timing of LEMTRADA exposure will be provided for the retrospectively collected pregnancy cases.

Additional supportive analyses will be documented in the statistical analysis plan (SAP).

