9 RESEARCH METHODS

9.1 STUDY DESIGN

This post authorization safety study (PASS) is an international, observational cohort (registry) of pregnancy outcomes in women with MS exposed to LEMTRADA during pregnancy.

Pregnancy outcomes in women exposed to LEMTRADA will be compared with available data from external comparison groups: women with MS not exposed to LEMTRADA, and women without MS (details defined in Section 4, under "Data source").

This is an observational study with no experimental intervention utilized. Women enrolled in the study may receive treatment and evaluations for their MS and their pregnancies as determined by their treating physicians in accordance with local standard of care. Information of prospective pregnancies on patient's safety and pregnancy outcome will be collected during each trimester and within 6 weeks after the end of pregnancy. For all live births, the infant's HCP will be contacted at 1 year post delivery to obtain follow-up on the infant's health status. Information of retrospective pregnancies (exposed to LEMTRADA during pregnancy but pregnancy outcome is known at time of registry) will be collected similarly except for information on the chronological interview during pregnancy.

Women who were pregnant or became pregnant within the period of time between their initiating a course of treatment with LEMTRADA to 4 months after their last infusion for that course may be enrolled, provided their pregnancy is ongoing.

A total of approximately 204 women exposed to LEMTRADA during pregnancy (prospective) will be enrolled to achieve approximately 193 women followed up to 1 year post-delivery. Retrospective pregnancies are not part of this sample size calculation and are collected additionally.

Women exposed to LEMTRADA during pregnancy will be recruited from a variety of sources, including referral of female patients who become pregnant while enrolled in a separate observational study; referral of LEMTRADA-exposed female patients reporting pregnancies identified through routine pharmacovigilance activities, and LEMTRADA-exposed female patients reporting pregnancies identified through study outreach activities such as study postings on applicable websites. Enrollment as early in the pregnancy as possible is encouraged. Study enrollment is voluntary and requires informed consent in accordance with local requirements.

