14 APPENDICES

Appendix A Description of pregnancy outcomes

Each defect will be categorized using the CDC MACDP classification of birth defects (CDC MACDP, 1998). Major defects identified from the point of conception up to 1 year of age will be included in the analysis. Defects identified in any live birth will be considered in the primary analysis. Defects identified in any stillbirths or abortions (spontaneous or induced) will be considered in secondary analyses.

MACDP defines major structural or genetic birth defects as conditions that

- 1. result from a malformation, deformation, or disruption in one or more parts of the body, a chromosomal abnormality, or a known clinical syndrome;
- 2. are present at birth;
- 3. have a serious, adverse effect on health, development, or functional ability.

A **minor** structural defect is defined as a defect which occurs in less than 4 percent of the population but which has neither cosmetic nor functional significance to the child (e.g., complete 2,3 syndactyly of the toes).

Spontaneous abortion

Any loss of a fetus due to natural causes at \leq 20 weeks gestation determined from the estimated date of conception or by ultrasound as spontaneous abortion. If available, information from gross or pathological examination of the abortus or fetus will be documented.

Induced abortion

Pregnancy termination is defined as any induced or voluntary fetal loss. If available, information from gross or pathological examinations will be documented.

Preterm birth

A live birth that occurs before 37 completed weeks of gestation determined from the estimated date of conception. Elective caesarian deliveries or inductions prior to 37 completed weeks will be analyzed separately.

Small for gestational age

Birth size (weight, length, or head circumference) ≤10th percentile for gender and gestational age using the NCHS pediatric growth curves for full term infants. Prenatal growth curves will be used for preterm infants.

Property of the Sanofi Group - strictly confidential

Stillbirth

Any non-deliberate foetal death at >20 weeks gestation as estimated based on the estimated date of conception or by ultrasound.

Lost to follow-up

Enrolled women will be considered lost to follow-up if they are eligible, have provided informed consent, and have completed the initial intake interview but pregnancy outcome information is not available within 1 year of the estimated delivery date despite 4 attempts to obtain this information.

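### The primary spontaneous-abortion relative risk takes no account of gestational age at enrolment, so a difference in entry timing between the cohorts could distort it by as much as the effect sought

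*Protocol*

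**What the plan says.** - **Endpoint and contrast** (Protocol 9.7.4.1): "Main criterion is rate of spontaneous abortion in the prospectively collected LEMTRADA-exposed group versus comparison cohorts".
- **Method** (9.7.5): each comparison is made "by calculating the relative risk (RR) and its 95% CIs", with exact methods where applicable. Section 9.5.1 sizes the study on a one-sided Fisher's exact test of two proportions, which confirms that the main comparison is a crude one.
- **Denominator** (9.7.1, repeated in 9.2.3): "The primary analysis population will include all women enrolled in the study prospectively who meet the study inclusion criteria and have pregnancy outcome data recorded". Gestational age at entry plays no part.
- **Entry** (9.1): exposed women "may be enrolled, provided their pregnancy is ongoing". The inclusion criteria in 9.2.2.1 set no upper gestational age. Early enrolment is encouraged, and Table 2 places the enrolment interview before 13 weeks only as an ideal.
- **Event window** (Appendix A): natural loss up to "20 weeks gestation determined from the estimated date of conception or by ultrasound as spontaneous abortion".
- **Delayed entry** (9.7.5): "A supportive analysis of (prospective) spontaneous abortion as a time-to-event endpoint will be conducted using the Kaplan-Meier method adjusting for left-truncation". A Cox model, if data are available, "may be used in the Cox regression context with left-truncation to adjust for potential confounding factors, such as gestational age at enrollment".
- **Comparators** (9.7.4.3): gestational age at enrolment is on the variable list for Cohorts II and III. Gestational age at the end of pregnancy is not.

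**The concern.** A woman who enrols with an ongoing pregnancy at week g has already survived to week g. She can contribute only the SAB risk between g and 20 weeks, and after 20 weeks she can contribute none. The primary proportion nevertheless gives every woman the same weight in the denominator. Each group's crude SAB proportion is then a mixture of its underlying risk and its own entry times, and the RR is a clean contrast only if the entry times are alike.

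Nothing in the design secures that. Exposed women are recruited internationally through referral from other studies, pharmacovigilance reports and outreach (9.2.4.2). Cohorts II and III come from a separate North American registry (9.3). No matching on entry week is required for the primary comparison, and the limitations in 9.9 discuss selection bias without naming delayed entry.

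In a safety study both directions matter. Later entry of exposed women can hide a real increase in fetal loss, and earlier entry can make a harmless exposure look harmful. A lesser problem of the same kind is that elective terminations are recorded outcomes and so stay in the crude denominator as non-events, although they end the time at risk.

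**Working it through.** **Inputs from the protocol (9.5.1, 9.5.2).** Exposed 204 × 0.95 = 193.8, stated as 193. Comparator 125 × 0.96 × 0.98 = 117.6, stated as 117. Background SAB 13.5%, RR 2.0 (so 27% exposed), one-sided Fisher's exact test at 0.025, stated power 80%.

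**Step 1: the plan's own figure.** Exact enumeration with 27% of 193 against 13.5% of 117 gives power 78.1%, close enough to the stated 80%. This is the reference below.

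**Step 2: enrolment after 20 weeks.** If a share s of a group enrols after week 20, its crude risk is multiplied by (1 − s). This needs no assumption about when losses occur; s itself is assumed. True RR is 2.0.

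| s | Exposed only late: crude RR | Power | Both groups late: crude RR | Power |
|---|---|---|---|---|
| 0 | 2.0 | 78% | 2.0 | 78% |
| 10% | 0.243/0.135 = 1.8 | 59% | 0.243/0.1215 = 2.0 | 71% |
| 20% | 0.216/0.135 = 1.6 | 37% | 0.216/0.108 = 2.0 | 64% |
| 30% | 0.189/0.135 = 1.4 | 18% | 0.189/0.0945 = 2.0 | 57% |

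**Step 3: a two-week difference in entry before 20 weeks.** The protocol gives no distribution of losses by week, so two assumed shapes bracket the answer.

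- *Front-loaded*: a fraction S of all losses to week 20 has occurred by entry, with S = 0.45 at week 8 and 0.70 at week 10. Remaining risk = p(1 − S)/(1 − pS). With p = 0.135: week 8, 0.07425/0.93925 = 7.9%; week 10, 0.0405/0.9055 = 4.5%.
- *Constant hazard from week 4 to week 20*: remaining risk = 1 − (1 − p)^((20 − w)/16). Week 8, 1 − 0.865^0.75 = 10.3%; week 10, 1 − 0.865^0.625 = 8.7%.

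| Scenario | Front-loaded | Constant hazard |
|---|---|---|
| No effect; exposed week 10, comparator week 8 | RR 0.57 | RR 0.84 |
| No effect; exposed week 8, comparator week 10 | RR 1.77, false positive about 15% | RR 1.19, false positive about 4.5% |
| True RR 2.0; exposed week 10, comparator week 8 | RR 1.26, power 6% | RR 1.73, power 39% |
| True RR 2.0; both week 8 | RR 2.14, power 58% | RR 2.04, power 65% |
| True RR 2.0; both week 10 | RR 2.23, power 35% | RR 2.06, power 58% |

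False-positive probabilities are for the one-sided test at nominal 2.5%.

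**Step 4: a four-week gap (week 8 against week 12), no drug effect.** Under a constant hazard, or one falling by a factor exp(−0.2) per week, the crude RR is 0.68 or 0.40 when exposed women enter later. It is 1.47 or 2.49 when they enter earlier. At its upper end this exceeds the two-fold effect for which the study is sized.

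**The case against.** A reader might infer that the primary result measures enrolment timing as much as drug effect. The protocol does not support that. It gives no entry-time distribution for either group, and the comparison cohorts also enrol during pregnancy, so similar timing would largely cancel in the ratio: step 3 gives 2.04 to 2.23 for a true 2.0. The one-sided late-enrolment figures in step 2 likewise need exposed women, and not comparators, to enrol late. That objection stands, which is why the claim is conditional and the symmetric case is shown beside it.

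It also stands that the loss-timing shapes are assumptions and that the result is sensitive to them. Under a constant hazard a two-week gap moves a null RR only to 0.84 or 1.19. A false signal is then made more likely, not certain. The power loss under equal entry may be overstated as well: some background rates cited in 9.5.1 (11.5% and 12.4%) come from prospective or registry cases and may already reflect delayed entry.

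Finally, the sponsor has not overlooked the problem. The left-truncated Kaplan-Meier analysis is committed to, and the Cox model names gestational age at enrolment. The dispute is over which analysis ranks first. This lowers the severity but does not remove the defect. Nor is the ranking left open for the SAP: the protocol itself calls the left-truncated analysis supportive and the Cox adjustment optional. No termination rate is given, so the effect of counting terminations as non-events cannot be sized.

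**Conclusion.** The point holds in conditional form. As written, the primary SAB comparison counts women who can no longer have the event and gives full weight to women who have passed part of the risk period. If the groups differ in gestational age at entry, the RR can move by an amount comparable with the two-fold effect sought: down to 1.4 for a true 2.0 if 30% of exposed women alone enrol after week 20, and to anywhere from 0.57 to 1.77 under no effect for a two-week gap with front-loaded losses (0.84 to 1.19 with a constant hazard). If entry timing is equal, the RR is nearly unbiased and the cost is mainly power. Late shares, entry weeks and loss-timing shapes are all assumptions, so the actual size and direction of bias cannot be known from the protocol. Severity: should-fix.

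**What to change.** - **9.2.3, 9.7.1 and 9.7.5:** restrict the SAB risk set to women enrolled before 20 weeks, in the exposed group and in Cohorts II and III alike.
- **9.7.5:** make the left-truncated analysis the primary SAB comparison, with gestational age as the time scale, entry at enrolment and follow-up to 20 weeks. Treat elective termination as a competing event (for example, Aalen-Johansen cumulative incidence with a Cox model for the contrast). Keep the crude RR, restricted to women enrolled before 20 weeks, as supportive.
- **9.7.4.3:** add gestational age at pregnancy end to the comparator variables.
- **9.6.5:** it excludes women lost to follow-up from outcome denominators. Reconcile this with censoring at last contact in the SAB analysis.
- **9.5.1:** state that the Fisher-based power refers to the crude comparison and is only approximate for the new primary analysis.

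The cost is mostly wording, because the analysis is already planned and comparator gestational age at enrolment is already listed. The extra data item is comparator gestational age at pregnancy end. The statistical price is that early risk sets are small, so the interval will be wider than the crude one. How much wider cannot be computed without the entry-time distribution.

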9.2.3 Analysis population(s)

The primary analysis population will include all women (prospectively) enrolled in the study who meet the study inclusion criteria and have pregnancy outcome data recorded. Outcomes for the primary analysis population will primarily be compared with pregnancy outcomes in unexposed external comparison groups.

Ascertainment of pregnancy outcomes will be considered completed when:

- Pregnancy outcome is known and was not a live birth, or
- Pregnancy outcome was a live birth and the 1-year post-delivery follow-up has been completed, or
- The woman has been classified as lost to follow-up, or
- The woman has withdrawn informed consent prior to ascertainment of pregnancy outcome.

Otherwise; the pregnancy outcome will be considered as pending.

For the analysis, descriptive analyses of baseline characteristics of the additional populations of all enrolled women (including women whose pregnancy outcome data are unknown, such as lost to follow up), and the subset of women whose pregnancy outcome data are unknown, will also be calculated.

Retrospective pregnancy population will provide qualitative data which will be descriptively analyzed independent of the prospectively collected primary analysis population.

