9.5 STUDY SIZE

9.5.1 Determination of sample size (LEMTRADA exposed)

The sample size of approximately 204 women exposed to LEMTRADA during pregnancy (prospective) is expected to achieve approximately 193 women followed up to 1 year post-delivery, allowing approximately 5% of recruited women to have missing pregnancy outcome data. With this sample size and a sample size of 117 in the comparator group, at 80% power and a 1-sided two-sample test with significance level of 0.025, we will be able to detect a 2.0-fold higher relative risk for a background spontaneous abortion rate of 13.5%, which encompasses the likely risk range for spontaneous abortions amongst women in the reference cohorts. In the reference cohorts of pregnancies from women with and without MS who were not exposed to LEMTRADA, where the rates of spontaneous abortion is expected to be 16.6% for women without MS (3) and 11.5% - 19.5% for women with MS (4,5,6). Retrospective pregnancies are not part of this sample size calculation and are collected additionally.

Table 1 shows the type of differences that may be detected comparing LEMTRADA-exposed pregnancies with various background rates for spontaneous abortion and any birth defects. For purposes of sample size calculation, a combination of general population background rates and rates published in the literature for women with MS with pregnancies unexposed to disease-modifying therapy were used.

16-Nov-2016 Version number: 1

Table 1 - Sample Size and Detectable Effect Size for Selected Endpoints

Endpoint	Population	Background Rate	Total Sample size	RR
Spontaneous abortion	General population	16.6% (3)	204 (Effective 193)	1.86
	Women with MS	11.5% (5)	204 (Effective 193)	2.12
	Women with MS	19.5% (4)	204 (Effective 193)	1.77
	Background Comparator Groups	13.5%	204 (Effective 193)	2.0
Any major birth defect General population		3% (8,9)	204 (effective 154)	4.05
	Women with MS	3% (10)	204 (effective 154)	4.05

RR: Relative Risk.

Sample size calculations were performed using EAST software version 6.2.

Assuming 5% drop out (outcome unavailable): 204*95%=193 patients will permit detection of RR=2.0 for a background rate of 13.5% with 80% power and 0.025 significance level based on 1-sided two sample Fisher's exact test (with comparator group sample size =117)

Assuming 80% live birth, 193*80%=154 live births.

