9.6 DATA MANAGEMENT

9.6.1 Data collection schedule

Table 2 - study data collection schedule

Data collected/ Evaluation	Enrolment Interview (ideally <13 weeks' gestation)	2nd Trimester Interview (16-20 weeks' gestation)	3rd Trimester Interview (26-32 weeks' gestation)	Pregnancy Outcome Interview (within 6 weeks after the end of the pregnancy) ab	Infant Status Update (1 year after delivery) b	Targeted Follow- up (after BDE review ^C	Retrospective Pregnancy (pregnancy outcome known at time of enrollment)
Enrollment and Informed Consent	Х						Χ
Contact Information and Demographics	X						Х
Targeted Medical History	X					X	Χ
Pregnancy History	X						Χ
Risk Factors d	X	X	X			Χ	Χ
LEMTRADA Exposure History ⁶	X						X
Concomitant Medications ^f	X	Х	Х	Х			X
Pregnancy Status/Outcome		Х	Х	X		Х	Х
Foetal/Pediatric Outcomes				Х	X	Х	Х
Medical Record Review of Pregnancy Outcome				Х		Х	Х
HCP Questionnaire on Infant Status at 1 Year					Χg		Х
Collection of selected adverse events ^h	Х	Х	Х	Х	Х	Х	Х

- a The interview can be conducted by phone or in person. Whenever medical documentation is needed (summary from maternity, other hospitalization or investigation summaries, etc.), they can be collected by electronic transfer
- b Active contact by national Coordinator, if needed, not later, than 6 weeks after expected delivery date and 1 year after delivery for live birth
- c Obtain this information if information is requested following Birth Defect Evaluator review
- d Risk factors: Smoking, alcohol use, illicit drug use, pre-pregnancy body mass index (BMI), etc....
- e Exposure history for current pregnancy only
- f All medications for MS from the onset, also other medications relevant to the disease or ongoing within 1 month to inclusion
- g For live-birth outcomes only, if woman has not withdrawn consent
- h AEs to be reported include: a) all serious adverse events, including medically important events and pregnancy outcome related events such as all major and minor malformations, spontaneous abortions, stillbirths, elective terminations, neonatal deaths ,preterm birth, small for gestational age at birth, and any other adverse pregnancy outcomes occurring in a LEMTRADA-exposed pregnancy; b) non serious AEs, which to the opinion of HCP or National Coordinator may potentially have impact on the outcome of the pregnancy, whether causally related to the drug product or not.

NOTE: BDE=Birth Defect Evaluator

Property of the Sanofi Group - strictly confidential

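### The main spontaneous-abortion comparison is a crude proportion over women who enrol at any gestational week, so a difference in enrolment timing between registries would be read as drug effect; the left-truncated analysis should lead

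*Protocol*

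**What the plan says.** **Main comparison.** Protocol 9.7.4.1: "Main criterion is rate of spontaneous abortion in the prospectively collected LEMTRADA-exposed group versus comparison cohorts of pregnancies". Section 9.7.5 compares rates "by calculating the relative risk (RR) and its 95% CIs", with exact methods when applicable, separately against each comparison group. Section 9.5.1 sizes the study with a one-sided Fisher test on two proportions.

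**Denominator.** Section 9.2.3, repeated in 9.7.1: "The primary analysis population will include all women (prospectively) enrolled in the study who meet the study inclusion criteria and have pregnancy outcome data recorded". No gestational-age limit is set.

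**Entry.** The inclusion criteria (9.2.2.1) set no upper gestational week. Section 9.1 admits any exposed woman whose pregnancy is ongoing. The only target is in Table 2 (9.6.1): "Enrolment Interview (ideally <13 weeks' gestation". Pregnancies whose outcome is already known at enrolment are retrospective and are described separately.

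**Event window.** Appendix A defines SAB as a natural loss at or before 20 weeks.

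**Handling of entry time.** Section 9.7.5: "A supportive analysis of (prospective) spontaneous abortion as a time-to-event endpoint will be conducted using the Kaplan-Meier method adjusting for left-truncation". So the method is planned, but in a supporting role. The regression version is optional and depends on what data can be had: "propensity score matching and covariate adjustment may be used in the Cox regression context with left-truncation to adjust for potential confounding factors". Gestational age at enrolment is the first confounder named there, and 9.7.4.3 lists it among the variables obtained for Cohorts II and III.

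**The concern.** A prospective woman is observed for SAB only from her enrolment week. One who enrols at week 7 has most of the risk window ahead of her, one who enrols at week 15 has little of it, and one who enrols after week 20 has none. The crude proportion gives all three the same weight. It therefore depends on the enrolment-week mix as well as on the hazard of loss.

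This would largely cancel if both groups enrolled at the same weeks, but nothing in the plan brings that about. The exposed women are recruited internationally through pharmacovigilance reports, referral from other studies and outreach (9.1, 9.2.4.2). Cohorts II and III come from a separate North American registry (9.3). If exposed women enrol earlier, the crude RR leans towards harm. If they enrol later, it leans towards reassurance. SAB is the primary outcome of a safety study, so either error matters, and the direction cannot be known in advance.

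**Working it through.** **Inputs from the protocol.** 193 exposed and 117 comparator women, background rate 13.5%, RR 2.0, one-sided Fisher test at 0.025 (9.5.1, 9.5.2); SAB up to week 20 (Appendix A).

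**Inputs that are assumed.** The weekly hazard of loss and the enrolment-week distributions, neither of which the protocol gives.

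**1. The plan's own figure.** The exposed rate is 2.0 × 13.5% = 27.0%. Exact power of the one-sided Fisher test for 27.0% v 13.5% with 193 v 117 is 78.1%, against 80% stated. The pooled normal approximation gives 81.3%, and Fisher power reaches 80% at RR 2.02. The stated figure is reproduced to within 2 points. Under the null (13.5% in both groups) the test rejects in 1.7% of studies.

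**2. Entry after week 20 only.** Let q1 and q0 be the shares of exposed and comparator women enrolled after week 20. None of them can have the event, so

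crude RR = true RR × (1 − q1) / (1 − q0).

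- q1 = 0.20, q0 = 0: a true RR of 1.0 reads 0.80. A true RR of 2.0 reads 1.6. If 13.5% is the rate in women enrolled by week 20, power is then 37%.
- q1 = 0, q0 = 0.20: a true RR of 1.0 reads 1/0.80 = 1.25. On the same condition the null rejection rate is 7.5%.
- To turn 1.0 into 2.0, or 2.0 into 1.0, needs a share of 0.50 in one group and none in the other.

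**3. Entry week inside the risk window.** The expected crude rate is the average, over enrolment week w, of

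1 − exp(−sum of weekly hazards from w to week 20).

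Enrolment week was assumed normal with SD 3 weeks. Four hazard shapes were assumed, each scaled so that the group with mean entry at week 8 has a crude rate of 13.5%.

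*No drug effect; exposed mean entry week 8, comparators later. Crude RR (chance of a significant Fisher test):*

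| Gap in mean entry | Steep decline | Moderate decline | Peak near week 8.5 | Flat |
|---|---|---|---|---|
| 1 week | 1.23 (7%) | 1.16 (5%) | 1.19 (6%) | 1.08 (3%) |
| 2 weeks | 1.53 (19%) | 1.36 (12%) | 1.48 (17%) | 1.18 (5%) |
| 3 weeks | 1.95 (38%) | 1.63 (23%) | 1.93 (37%) | 1.30 (9%) |
| 4 weeks | 2.52 (59%) | 1.96 (39%) | 2.63 (63%) | 1.45 (15%) |

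*True hazard ratio 2; comparator mean entry week 8, exposed later. Crude RR:*

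| Gap in mean entry | Steep decline | Moderate decline | Peak near week 8.5 | Flat |
|---|---|---|---|---|
| none | 1.82 | 1.84 | 1.83 | 1.86 |
| 3 weeks | 0.97 | 1.16 | 0.97 | 1.45 |
| 4 weeks | 0.76 | 0.97 | 0.72 | 1.30 |

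In the 4-week row, power is 12% or less under every shape.

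**4. Does left truncation repair it?** Simulation under the moderate-decline shape, 200,000 women per group, mean entry weeks 8 and 12, delayed-entry risk sets and a Mantel-Haenszel hazard ratio:

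- No effect, exposed women earlier: crude RR 2.01, left-truncated hazard ratio 1.02.
- True hazard ratio 2, exposed women later: crude RR 0.96, left-truncated hazard ratio 1.97.

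**The case against.** **The protocol does not ignore enrolment timing.** This stands. It commits to the left-truncated Kaplan-Meier analysis, names gestational age at enrolment as a confounder, obtains it for the comparators and encourages early enrolment. No decision rule acts on the crude RR alone, and both estimates will be reported. The dispute is about which one leads. But the protocol settles that question itself, so it is not a detail left to the SAP, and the limitations in 9.9 do not mention enrolment timing.

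**Counting late enrollees as event-free is an inference.** This also stands. No sentence says so. It follows from open enrolment, the stated denominator and the week-20 definition, unless the SAP adds an at-risk rule.

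**A reader might infer that the registries' enrolment weeks do differ, and that the RR will be off by a factor of two.** The documents do not support that. They give no enrolment-week distribution for either source. Gaps of 1 to 2 weeks give null RRs of 1.08 to 1.53, and a flat hazard stays well short of a doubling even at 4 weeks. Entry after week 20 needs about a 50% imbalance to do it alone.

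**A reader might also infer that the 80% power is wrong.** Section 9.5.1 says "we will be able to detect a 2.0-fold higher relative risk for a background spontaneous abortion rate of 13.5"%, and the calculation reproduces closely. How 13.5% was derived is not stated. Two of the MS rates cited in 9.5.1 are observed proportions from prospective pharmacovigilance cases (49/425) and a pregnancy exposure registry (28/226), and these may already reflect delayed entry. Diluting 13.5% again could count the same loss twice, so the 37% in step 2 of the working is conditional.

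**Conclusion.** The point holds as a weakness in the choice of main analysis. Following sections 9.7.4.1 and 9.7.5 as written lets enrolment timing enter the headline SAB estimate, while the method that removes it is ranked below and its covariate-adjusted form is optional.

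The mechanism follows from the protocol's own rules. The size does not: it rests on assumed hazards, an assumed SD of 3 weeks, and calibration to 13.5% at mean entry week 8. On those assumptions a gap of about 3 to 4 weeks in mean entry creates or hides roughly a doubling under declining or peaked hazards. A flat hazard gives about 1.45 at 4 weeks, and 20% late entry in one group alone gives 0.80 or 1.25. If the two sources enrol at similar weeks, the bias is small. The recovery by left truncation was checked under one hazard shape only.

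**What to change.** - **9.7.4.1 and 9.7.5:** make the left-truncated comparison the main SAB analysis against Cohorts II and III, with entry at gestational age at enrolment and follow-up to week 20. Report the crude RR as supportive.
- **SAB analysis set:** in both groups, limit it to women enrolled at or before week 20. The analysis sets for the other outcomes need not change.
- **9.5.1:** at most, add a note that the stated power applies if the 193 and 117 women are enrolled by week 20. No change to the figure is called for.

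**Cost.** The method is already planned and the enrolment week is already listed for Cohorts II and III, so no new data are needed. The price is a somewhat wider interval, a less familiar headline estimate, and a Fisher-based sample size that matches the main analysis only approximately. Women enrolled after week 20 would no longer count towards the SAB comparison.
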